4.2.3.6.1 Target Engagement (TE)

IL-10 target engagement will be assessed by measuring the total circulating IL-10, the combined total concentration of both free IL-10 and the IL-10 that is bound to MK-1966. IL-10 concentrations in serum will be measured using a qualified bioanalytical assay. As the concentration of free IL-10 is expected to be quite low (pg/mL) and the clearance rate of IL-10 bound to MK-1966 is expected to be slow, the target engagement assay is expected to measure primarily MK-1966 bound IL-10.

In previous studies with SD-101, the induction of IFN- α associated genes in the peripheral blood was used to determine target engagement and used for dose selection. IFN- α associated genes ISG-54, MX-b, IP-10 and MCP-1 were monitored and demonstrated to be upregulated greater than 3 fold (3 out of the 4 genes up-regulated at any time point). Dose dependency was observed from 0 to 1.0 mg but from 1.0 to 5.0 mg no dose dependency was observed. IFN- α was not consistently upregulated with SD-101 administration.

4.2.3.6.2 Anti-Drug Antibody (ADA) Assay

1) Screening ADA assay

ADA screening assay (including the Confirmatory test for specificity against the drug, and titer determination for confirmed positive samples) will be developed and validated

in human serum to support clinical studies. A standard bridging ECL assay with the required sensitivity and drug tolerance using MSD platform will be used.

The assay will be validated prior to FIH study start.

2) Neutralizing anti-drug antibody (NAb) assay

A non-cell-based NAb assay in human serum will be developed and validated for further characterization of confirmed ADA positive samples. The assay will be used to support the early phases of the FIH study. A cell based Nab assay will be developed and validated as well once an appropriate cell line is established to support the later phases of the FIH study.

4.2.3.6.3 Cytokines of Systemic Immune Activation

Due to immune stimulation by SD-101 and enhanced immune activation by the administration of SD-101, a panel of cytokine proteins will be monitored including IL-10, IFN- γ , IL-12p70, IL-13, IL-1 β , IL-2, IL-4, IL-6, IL-8, TNF- α and IFN- α 2a.

4.2.3.6.4 Exploratory RNA Profiling and IHC Markers

The relationship between anti-tumor activity of MK-1966 in combination with SD-101 will be investigated through evaluation of gene expression (including IFN- α) in blood and in pre and post biopsy tumor tissue. Responses will also be correlated to pre-treatment gene expression data with a goal to identify potential patient selection biomarkers.

Multiple immunohistochemistry (IHC) assays are planned and are currently in development to support exploratory biomarker research including CD3, CD8, pDC, TLR9 and PD-L1.

4.2.3.6.5 Exploratory Objective on the Longitudinal Change of Tumor Size

The longitudinal measurement on tumor size will be investigated to collect information on the tumor response to the treatment. Several statistical modeling methods will be explored to analyze tumor size longitudinally based on imaging assessment.

4.2.3.7 Planned Exploratory Biomarker Research

Planned Genetic Analysis

Understanding genetic determinants of drug response is an important endeavor during medical research. This research will evaluate whether genetic variation within a clinical trial population correlates with response to the treatment(s) under evaluation. If genetic variation is found to predict efficacy or adverse events, the data might inform optimal use of therapies in the patient population. This research contributes to understanding genetic determinants of efficacy and safety associated with the treatments in this study.

4.2.3.8 Future Biomedical Research

The Sponsor will conduct Future Biomedical Research on specimens collected for future biomedical research during this clinical trial. This research may include genetic analyses

(DNA), gene expression profiling (RNA), proteomics, metabolomics (serum, plasma) and/or the measurement of other analytes.

Such research is for biomarker testing to address emergent questions not described elsewhere in the protocol (as part of the main trial) and will only be conducted on specimens from appropriately consented subjects. The objective of collecting specimens for Future Biomedical Research is to explore and identify biomarkers that inform the scientific understanding of diseases and/or their therapeutic treatments. The overarching goal is to use such information to develop safer, more effective drugs/vaccines, and/or to ensure that subjects receive the correct dose of the correct drug/vaccine at the correct time. The details of this Future Biomedical Research sub-trial are presented in Section 12.2 - Collection and Management of Specimens for Future Biomedical Research. Additional informational material for institutional review boards/ethics committees (IRBs/ERCs) and investigational site staff is provided in Section 12.3.

4.3 Benefit/Risk

Subjects in clinical trials generally cannot expect to receive direct benefit from treatment during participation, as clinical trials are designed to provide information about the safety and effectiveness of an investigational medicine.

Additional details regarding specific benefits and risks for subjects participating in this clinical trial may be found in the accompanying IB and Informed Consent documents.

5.0 METHODOLOGY

5.1 Entry Criteria

5.1.1 Diagnosis/Condition for Entry into the Trial

Male/Female subjects with advanced malignancies, of at least 18 years of age will be enrolled in this trial.

5.1.2 Subject Inclusion Criteria

In order to be eligible for participation in this trial, the subject must:

1. Have one of the following diagnoses
 - a. A histologically- or cytologically-confirmed low grade B-cell lymphoma which has progressed after standard of care therapy/treatments and there is no available therapy likely to convey clinical benefit.
 - b. Unresectable melanoma that in the opinion of the Investigator have progressed after anti-PD-1 therapy, and/or anti-PD-1 and CTLA-4 combination treatments. Subjects who have BRAF V600 mutant melanoma are required to have had a prior treatment regimen that included vemurafenib, dabrafenib, or other approved BRAF and/or MEK inhibitor.
 - c. SCCHN that have progressed after standard of care therapy/treatments and there is no available therapy likely to convey clinical benefit. Subjects are

required to have been refractory to platinum (either cisplatin or carboplatin) and cetuximab. Resistance is defined as tumor progression or recurrence within 6 months of platinum or cetuximab therapy in the adjuvant (e.g. with radiation after surgery), primary (e.g. with radiation), recurrent, or metastatic setting. Subject must be resistant to both platinum and cetuximab.

- d. Breast cancer with dermal metastasis, which has progressed after standard-of-care therapy/treatments and there is no available therapy likely to convey clinical benefit.
- e. Part B will enroll subjects with unresectable melanoma that in the opinion of the Investigator have progressed after anti-PD-1 therapy, and/or anti-PD-1 and CTLA-4 combination treatments. Subjects who have BRAF V600 mutant melanoma are required to have had a prior treatment regimen that included vemurafenib, dabrafenib, or other approved BRAF and/or MEK inhibitor.
- f. Part C will enroll SCCHN that have progressed after standard of care therapy/treatments and there is no available therapy likely to convey clinical benefit. Subjects are required to have been refractory to platinum (either cisplatin or carboplatin) and cetuximab. Resistance is defined as tumor progression or recurrence within 6 months of platinum or cetuximab therapy in the adjuvant (e.g. with radiation after surgery), primary (e.g. with radiation), recurrent, or metastatic setting. Subject must be resistant to both platinum and cetuximab.

2. Subjects with melanoma, squamous cell cancer of head and neck or breast cancer with dermal metastasis must have a tumor accessible to intralesional injection and have measurable disease by Cheson or irRECIST criteria.
3. Subjects with B Cell Lymphoma must have:
 - a. Biopsy confirmed, low-grade B-cell lymphoma, including follicular (Grade 1, 2, or 3A [27]), or marginal, or CLL/SLL with lymph node involvement that has progressed after standard of care therapy/treatments and there is no available therapy likely to convey clinical benefit.
 - b. Measurable disease per Cheson criteria (1 lesion must measure at least 1.5 cm in any diameter or 1.0 cm in the shortest diameter if one of the diameters is not \geq 1.5 cm), and be palpable and easily accessible in a low-risk site (eg, inguinal, axillary, cervical, subcutaneous) for intratumoral injection.
4. Be \geq 18 years of age on day of signing informed consent.
5. Have a performance status of 0 or 1 on the Eastern Cooperative Oncology Group (ECOG) Performance Scale (Appendix 12.4).
6. Have a life expectancy \geq 6 months
7. Demonstrate adequate organ function as defined by the following table ([Table 4](#)). All screening labs should be performed within 7 days of treatment initiation.

Table 4 Adequate Organ Function Laboratory Values

System	Laboratory Value
Hematological	
Absolute neutrophil count	$\geq 1,500/\text{mcL}$
Platelets	$\geq 100,000/\text{mcL}$
Hemoglobin ^b	$\geq 9 \text{ g/dL}$ or $\geq 5.6 \text{ mmol/L}$
Renal	
Serum Creatinine or Creatinine Clearance (CrCl) (measured or calculated) ^a or Glomerular Filtration Rate (GFR) in place of CrCl	$\leq 1.5 \times \text{ULN}$ or $\geq 60 \text{ mL/min}$ for subject with creatinine levels $> 1.5 \times \text{ULN}$
Hepatic	
Total bilirubin (serum)	$\leq 1.5 \times \text{ULN}$ or Direct bilirubin $\leq \text{ULN}$ for subjects with total bilirubin levels $> 1.5 \times \text{ULN}$
AST (SGOT) and ALT (SGPT)	$\leq 2.5 \times \text{ULN}$ OR $\leq 5 \times \text{ULN}$ for subjects with liver metastases
Coagulation^c	
International Normalized Ratio (INR) or Prothrombin Time (PT) Activated Partial Thromboplastin Time (aPTT)	$\leq 1.5 \times \text{ULN}$ $\leq 1.5 \times \text{ULN}$

^a Creatinine clearance should be calculated per institutional standard
^b Hemoglobin should be without transfusion within 4 weeks of Day 1.
^c If the subject is receiving anticoagulant therapy, the PT or partial thromboplastin time (PTT) should be within the therapeutic range of intended use of anticoagulants.

8. Have voluntarily agreed to participate by giving written informed consent. The subject may also provide consent for Future Biomedical Research. However, the subject may participate in the main trial without participating in Future Biomedical Research
9. Female subjects of childbearing potential must have a negative urine or serum pregnancy test at Screening and again within 72 hours prior to receiving the first dose of study treatment. If the urine test is positive or cannot be confirmed as negative, a serum pregnancy test will be required. The serum pregnancy test must be negative for the subject to be eligible.
10. Female subjects of childbearing potential (refer to Section 5.7.2) must be willing to use an adequate method of contraception as outlined in Section 5.7.2– Contraception, for the course of the study through 120 days after the last dose of study medication.
 Note: Abstinence is acceptable if this is the usual lifestyle and preferred contraception for the subject.
11. Male subjects of childbearing potential (refer to Section 5.7.2) must agree to use an adequate method of contraception as outlined in Section 5.7.2– Contraception, starting with the first dose of study therapy through 120 days after the last dose of study therapy.

Note: Abstinence is acceptable if this is the usual lifestyle and preferred contraception for the subject.

12. Submit archived or fresh tumor sample during screening period as specified in the Procedures Manual.

5.1.3 Subject Exclusion Criteria

The subject must be excluded from participating in the trial if the subject:

1. Has had chemotherapy, radiation, or biological cancer therapy within 4 weeks prior to the first dose of study therapy, or who has not recovered to CTCAE grade 1 or better from the adverse events due to cancer therapeutics administered more than 4 weeks earlier.
2. Is currently participating and receiving study therapy or has participated in a study of an investigational agent and received study therapy or used an investigational device within 28 days of administration of MK-1966 or SD-101.
3. Is expected to require any other form of antineoplastic therapy while on study.
4. Is on chronic systemic steroid therapy in excess of replacement doses, or on any other form of immunosuppressive medication.
5. Has a history of a malignancy, unless potentially curative treatment has been completed, with no evidence of malignancy for 5 years.
 - a. Note: The time requirement for no evidence of disease for 5 years does not apply to the tumor for which a subject is enrolled in the study. The time requirement does not apply to subjects who underwent successful definitive resection of basal cell carcinoma of the skin, superficial bladder cancer or in situ cervical cancer.
6. Has known active central nervous system (CNS) metastases and/or carcinomatous meningitis. Subjects with previously treated brain metastases may participate provided they are clinically stable for at least 4 weeks prior to study entry, have no evidence of new or enlarging brain metastases and are off steroids.
7. Has had a severe hypersensitivity reaction to treatment with another monoclonal antibody.
8. Has an active autoimmune disease that has required systemic treatment in past 2 years (i.e. with use of disease modifying agents, corticosteroids or immunosuppressive drugs). Replacement therapy (e.g., thyroxine, insulin, or physiologic corticosteroid replacement therapy for adrenal or pituitary insufficiency, etc.) is not considered a form of systemic treatment.
9. Has an active infection requiring therapy.
10. Has active, current pneumonitis, or a history of (non-infectious) pneumonitis that required steroids.
11. Has had a prior stem cell or bone marrow transplant.
12. Is positive for Human Immunodeficiency Virus (HIV), Hepatitis B, or Hepatitis C.

13. Has a history or current evidence of any condition, therapy, or laboratory abnormality that might confound the results of the study, interfere with the subject's participation for the full duration of the study, or is not in the best interest of the subject to participate, in the opinion of the treating Investigator.
14. Has known psychiatric disorder(s) that would interfere with cooperation with the requirements of the trial.
15. Is a regular user, as determined by investigator judgment, (including "recreational use") of any illicit drugs or had a recent history (within the last year) of substance abuse (including alcohol), at the time of signing informed consent.
16. Has symptomatic ascites or pleural effusion. A subject who is clinically stable following treatment for these conditions (including therapeutic thoraco- or paracentesis) is eligible.
17. Is pregnant or breastfeeding, or expecting to conceive or father children within the projected duration of the study.
18. Has clinically significant heart disease that affect normal activities.
19. Has had major surgery (requiring at least a 3 day hospital stay) in the past 28 days.
20. Has received a live vaccine within 30 days prior to first dose.

5.2 Trial Treatment(s)

The treatment(s) to be used in this trial are outlined below in [Table 5](#).

Table 5 Trial Treatment for MK-1966 and SD-101

Treatment During Part A: Dose Finding					
Drug	Dose/Potency	Dose Frequency	Route of Administration	Regimen/Treatment Period ^{††}	Use
MK-1966	70 mg 210 mg 700 mg	Day 1, then Q3W	Intravenous over 30 -120 min	Day 1 then Q3W for 7 additional doses	Experimental
SD-101	1 mg 4 mg [†]	Days 1, 8, 15, 22 then Q3W	Intratumorally	Days 1, 8, 15, 22 then Q3W for 6 additional doses	Experimental
Treatment During Part B and C: Expansion Cohort					
Drug	Dose/Potency	Dose Frequency	Route of Administration	Regimen/Treatment Period ^{††}	Use
MK-1966	MTD/MAD	Every 3 weeks	Intravenous over 30 -120 min	Day 1 then Q3W for 7 additional doses	Experimental
SD-101	4 mg [†]	Days 1, 8, 15, 22 then Q3W	Intratumorally	Days 1, 8, 15, 22 then Q3W for 6 additional doses	Experimental

[†] Note, if the 4 mg SD-101 and 70 mg MK-1966 combination (cohort 2) is not tolerated, then the dose of SD-101 for subsequent cohorts (3 & 4) in part A and expansion cohorts (Parts B and C) will be 1 mg.

^{††}When MK-1966 and SD-101 are scheduled at the same time:

1. SD-101 will be administered first.
2. MK-1966 will be administered at least 30 minutes after the SD-101 injection.

Trial treatment should begin on the day of treatment allocation/randomization or as close as possible to the date on which the subject is allocated/assigned.

The investigator shall take responsibility for and shall take all steps to maintain appropriate records and ensure appropriate supply, storage, handling, distribution and usage of trial treatments in accordance with the protocol and any applicable laws and regulations.

5.2.1 Dose Selection/Modification

5.2.1.1 Dose Selection (Preparation)

Details on dose calculation, preparation and administration of MK-1966 and SD-101 are provided in the Pharmacy Manual.

5.2.1.2 Dose Escalation

Enrollment to Arm A, (MK-1966 with SD-101) will begin at the 70 mg for MK-1966 and 1 mg for SD-101. The initial dose combination of SD-101 and MK-1966 will test the tolerability of administering both agents in subjects with advanced tumors. The following three dosing cohorts were chosen with administration of the higher fixed dose of SD-101 to increase immune activation combined with escalating doses of MK-1966. All dose levels in Part A will follow 3+3 design. Dose escalation of MK-1966 will continue to identify a preliminary MTD or MAD.

The dosing for each cohort is as follows:

- 1) 1 mg SD-101 intratumorally and 70 mg MK-1966 intravenously
- 2) 4 mg SD-101 intratumorally and 70 mg MK-1966 intravenously
- 3) 4 mg SD-101 intratumorally and 210 mg MK-1966 intravenously
- 4) 4 mg SD-101 intratumorally and 700 mg MK-1966 intravenously

Note, if the 4 mg SD-101 and 70 mg MK-1966 combination (cohort 2) is not tolerated, then SD-101 will be de-escalated to a 1 mg dose for subsequent cohorts (3 & 4). The study will include up to four dosing cohorts for SD-101 and MK-1966.

5.2.1.2.1 3+3 Dose Escalation

During 3+3 dose escalation, at least 2 days of observation will occur between each of the first 3 subjects at each dose level.

Dose escalation will increase in increments of approximately 3 fold.

The rules applied for the preliminary dose finding using the 3+3 design are as follows:

An initial cohort of 3 subjects is enrolled.

- If 0/3 subjects develops a DLT, escalation to the next dose will occur.
- If 1/3 subjects develops a DLT, another 3 subjects will be enrolled at this dose level.
 - If 0 of the 3 new subjects develops a DLT (for a total of 1/6 subjects with a DLT at this dose level), escalation to the next dose level will occur.

- If ≥ 1 of the 3 new subjects develops a DLT (for a total of $\geq 2/6$ subjects with a DLT at this dose level), the dose escalation stage of the trial will be terminated.
- If $\geq 2/3$ subjects develop a DLT, the dose escalation stage of the trial will be terminated. If the dose directly below the current dose had been studied in at least 3 subjects, the dose directly below the current dose will be considered the preliminary MTD, and the study will proceed to the confirmation/expansion stage. It is conceptually acceptable to de-escalate to an intermediate, not pre-defined and not previously-studied dose, if evaluation of toxicity at such a dose is desired in lieu of proceeding directly to the dose confirmation/expansion stage of the study. If this approach is taken, 3 new subjects should be enrolled at the new intermediate dose, and the aforementioned rules should be used to determine further enrollment at this dose level.
- If the highest candidate dose of MK-1966 is studied during dose escalation, and 0/3 subjects or $<2/6$ subjects develop a DLT at that dose, then dose escalation will terminate with this finding and this dose level will be taken to the confirmation/expansion stage.

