2.0 TRIAL DESIGN

2.1 Trial Design

This is a non-randomized, multi-site, open-label trial of MK-1966 in combination with SD-101 in subjects with B-cell lymphoma, melanoma, squamous cell cancer of head and neck (SCCHN), breast cancer with dermal metastasis (see Section 5.1.2 for enrollment criteria). This trial will use an adaptive design based on the pre-specified criteria of dose limiting toxicity (DLT). For Dose Escalation (Part A) a 3+3 dose escalation design will be utilized (See Section 5.2.1.4). For Dose Confirmation (Parts B and C) the toxicity probability interval (TPI) design [1] will be utilized to refine the estimate of MTD.

In Part A, MK-1966 will be given in combination with SD-101 and will enroll subjects with one of the four potential malignancies described above. Enrollment to each dose level in Part A will occur sequentially, with each successively higher dose level initiating if the preceding dose is deemed tolerable per the DLT criteria (see Section 5.2.2). Subjects will continue at their enrolled dose for the duration of their participation. The study will begin with a 3+3 design to identify a preliminary MTD or MAD of the combination. During 3+3 dose escalation, an initial cohort of 3 subjects will be enrolled to a dose level. If none of the 3 subjects experience a DLT, escalation to the next dose will occur. If one of the 3 subjects experiences a DLT, another 3 subjects will be enrolled at this dose level. If 1 DLT is observed among the 6 subjects, the dose escalation will continue. If $\geq 2/3$ or $\geq 2/6$ subjects at a dose level develop DLTs, dose escalation will be terminated, and the study will proceed to the dose confirmation stage at the previous dose level. At least 2 days of observation will occur between each of the first 3 subjects in the first 2 dose levels.

In Parts B and C, dose confirmation will refine the estimate of the tolerability of the MTD/MAD, using a toxicity probability interval. Enrollment to Parts B and C will occur in parallel with treatment allocation accomplished by non-random assignment to either part. Part B will enroll subjects with melanoma and Part C will enroll subjects with SCCHN (see Section 5.1.2 for enrollment criteria).

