4.2.2.2 Rationale for SD-101 Dose

SD-101 being a TLR9 agonist is expected to induce high levels of IFN- α that may be responsible for anti-tumor effects. IFNs can directly inhibit the proliferation of tumor cells and increase major histocompatibility complex (MHC) class I expression, enhancing antigen recognition. Additionally IFNs have potent effects on tumor infiltrating leukocytes, including enhancing antigen presenting function of dendritic cells, increasing the effector function of T-cells, and activating cytotoxic activity of natural killer cells [23].

The 1 mg and subsequently the 4 mg fixed intratumoral dose of SD-101 is based on previous clinical studies conducted with subcutaneously dosing of SD-101 (DV3-HNV-01, DV3-HCV-01), ongoing clinical study with intratumoral dosing (DV3-LYM-01), mechanism of action, and nonclinical studies with SD-101. The 1 mg dose of SD-101 was chosen as the starting dose as it demonstrated good safety and tolerability in the subjects with lymphoma and will allow a safety margin if co-administration with MK-1966 enhances its potential effects. If treatment with the 1 mg dose of SD-101 and the lowest dose of MK-1966 is tolerated the next cohort will receive a 4 mg dose of SD-101 with the lowest dose of MK-1966. If treatment with 4 mg of SD-101 and the lowest dose of MK-1966 is not tolerated in cohort 2, further dosing with SD-101 will continue at the de-escalated dose of 1 mg.

Based on data from a study in healthy male volunteers (DV3-HNV-01), elevation of biomarkers was seen after a single 0.1 mg subcutaneous dose and increased with doses up to 5 mg. From limited PK data after subcutaneous administration, maximum mean plasma levels were comparable at 3.0 mg ($C_{max} = 7 \text{ ng/mL}$; $n = 6$) and 5.0 mg ($C_{max} = 6 \text{ ng/mL}$; $n = 2$) doses (DV3-HNV-01 CSR). SD-101 demonstrated a dose-dependent IFN- α -inducible gene and serum protein biomarker response. AEs were limited to flu-like symptoms and administration-site pain and induration. Data from DV3-HCV-01 suggest that SD-101 appears to be generally safe and well tolerated with weekly subcutaneous doses of 0.1 mg, 1.0 mg, 3.0 mg, and 5.0 mg (DV3-HCV-01 CSR).

A summary of the clinical studies conducted to date with SD-101 is provided in the IB. For further information, see the IB.

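### If cohort 2 (4 mg SD-101 + 70 mg MK-1966) fails, one rule ends Part A and another continues it; the stopping rule needs a cohort-2 exception

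*Combined protocol and SAP*

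**What the plan says.** **Scope.** Section 5.2.1.2 lists four Part A cohorts (SD-101 + MK-1966): 1 mg + 70 mg, 4 mg + 70 mg, 4 mg + 210 mg and 4 mg + 700 mg. It places all of them under one scheme: "All dose levels in Part A will follow 3+3 design. Dose escalation of MK-1966 will continue to identify a preliminary MTD or MAD".

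**Stop.** For 2 or more DLTs in 3 or 6 subjects at a dose level, Section 2.1 says "dose escalation will be terminated, and the study will proceed to the dose confirmation stage at the previous dose level". Section 5.2.1.2.1 repeats this for the six-subject case ("subjects with a DLT at this dose level), the dose escalation stage of the trial will be terminated"). For the three-subject case, provided the lower dose has been given to 3 or more subjects, it adds that "the dose directly below the current dose will be considered the preliminary MTD, and the study will proceed to the confirmation/expansion stage". None of this text makes an exception for cohort 2 or refers to the Note.

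**Continue.** The Note in Section 5.2.1.2 says that if cohort 2 is not tolerated, "then SD-101 will be de-escalated to a 1 mg dose for subsequent cohorts (3 & 4"). The Table 5 footnote in Section 5.2 agrees ("then the dose of SD-101 for subsequent cohorts (3 & 4) in part A") and extends the 1 mg dose to Parts B and C. The SD-101 dose rationale (Section 4.2.2.2) says that "further dosing with SD-101 will continue at the de-escalated dose of 1 mg".

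**The concern.** Section 2.1 judges tolerability by the DLT criteria. Failing to tolerate cohort 2 and meeting the 3+3 stopping count are therefore the same event, and the protocol attaches two instructions to it. Cohorts 3 and 4 cannot open if escalation has ended.

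The primary objective is to establish an MTD or MAD. Under the stopping text, 70 mg + 1 mg becomes the preliminary MTD, and MK-1966 escalation in Part A ends because of a failure that followed a rise in SD-101 alone. Under the Note, 3+3 continues at 210 mg + 1 mg.

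The Note also leaves a gap. If 210 mg + 1 mg then fails, Section 5.2.1.2.1 names the dose directly below as the preliminary MTD. In the listed cohort order that could be read as cohort 2, the combination that has just failed.

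**Working it through.** **1. Can the texts be reconciled?** Following both texts after a cohort-2 failure:

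| | Stopping text (2.1, 5.2.1.2.1) | Note and Table 5 footnote |
|---|---|---|
| Part A | ends | continues under 3+3 |
| Next dose | 70 mg + 1 mg, in confirmation | 210 mg + 1 mg, in Part A |
| MK-1966 range left in Part A | none | 210 and 700 mg |

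One clause in Section 5.2.1.2.1 might seem to bridge them: "It is conceptually acceptable to de-escalate to an intermediate, not pre-defined and not previously-studied dose". It does not. It covers moving down to a dose that was not pre-defined. The Note moves MK-1966 up, to a pre-defined level, with SD-101 at 1 mg.

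**2. The plan's own totals.** Scenario 1: 4 × 3 + 20 + 20 = 52. Scenario 2: 4 × 6 + 20 + 20 = 64. Both reproduce. With 40 subjects in Parts B and C, a cohort-2 failure gives at most 12 + 40 = 52 under the stopping text and at most 24 + 40 = 64 under the Note. The planning figure of 64 is unaffected.

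**3. How often would it matter?** A dose level with true DLT rate p passes 3+3 with 0/3, or with 1/3 followed by 0/3:

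P(pass) = (1−p)³ + 3p(1−p)² × (1−p)³

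| p | P(pass) | P(stop) = 1 − P(pass) |
|---|---|---|
| 0.05 | 0.973 | 0.027 |
| 0.10 | 0.906 | 0.094 |
| 0.20 | 0.709 | 0.291 |
| 0.30 | 0.494 | 0.506 |

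The documents give no DLT rates for the combination, so the rates below are assumptions.

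- The conflict arises when cohort 1 passes and cohort 2 stops: P(pass, cohort 1) × P(stop, cohort 2).
- The preliminary MTDs differ when, in addition, 210 mg + 1 mg passes. If it fails, the Note path sensibly falls back to cohort 1, the same dose as the stopping text gives.

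| Assumed rates: cohort 1 / cohort 2 / 210 mg + 1 mg | Conflict arises | Preliminary MTDs differ |
|---|---|---|
| 5 / 10 / 10% | 0.973 × 0.094 = 0.091 | 0.091 × 0.906 = 0.083 |
| 10 / 20 / 20% | 0.906 × 0.291 = 0.264 | 0.264 × 0.709 = 0.187 |
| 10 / 30 / 30% | 0.906 × 0.506 = 0.458 | 0.458 × 0.494 = 0.227 |

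If cohorts 1 and 2 both have a 5% rate, the conflict arises with probability 0.973 × 0.027, about 2.6%.

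**The case against.** **The intent is clear.** The rule that dosing continues at 1 mg SD-101 is stated in three places, one of them in the parent section of the 3+3 rules. A cohort-specific instruction normally overrides a general one. The sponsor and principal investigators review each cohort before the next opens (Section 7.1.2.1), and nothing suggests the sponsor would act against its own Note. This stands as a reason to expect the Note to be followed. It does not make the stopping text correct, and the choice would be made after DLTs were seen, open-label and with no external safety reviewer.

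**The percentages are not a risk of harm.** They give the chance that two texts, each followed mechanically, lead to different doses. The chance of a wrong decision is smaller, because most readers would follow the Note. Rates below those assumed are also plausible: Section 4.2.2.2.1 reports no DLT with single-agent intratumoral SD-101 up to 8 mg. Both points stand.

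**Confirmation may reach the same dose.** Section 5.2.1.2.2 lets the TPI design move along MK-1966 doses with SD-101 fixed, and counts Part A subjects at the selected dose. Table 6 says escalate at 0/5. If cohort 1 was 0/3, two further DLT-free subjects would open 210 mg + 1 mg, with chance 0.95² = 90% or 0.90² = 81% at the assumed cohort-1 rates. So the final dose may differ less often than the preliminary one. The routes are still not equivalent. First exposure to 210 mg + 1 mg could then fall in Parts B and C, where enrollment is continuous until a DLT is seen, and not in a 3-subject cohort that is reviewed before the next one opens.

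**An exception would remove the intermediate-dose option.** This does not stand. The Note already fixes SD-101 at 1 mg for cohorts 3 and 4.

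**Conclusion.** The concern holds, for cohort 2 only. Nothing contradicts the stopping rule at the other three cohorts. For cohort 2 the unconditional stopping text gives the wrong next step and the wrong preliminary MTD, taking the Note as the intended rule.

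Over the three assumed sets of DLT rates, the conflict arises in about 9% to 46% of trials, and the preliminary MTD differs in about 8% to 23%. The starting MK-1966 dose for Parts B and C is then 70 mg under the stopping text and 210 or 700 mg under the Note. These figures depend on the assumed rates and on literal application of each text. The practical risk is lower, because the Note would probably be followed and TPI movement could later bring the two paths together. No sample size, interval or analysis in the plan is wrong because of this. It should still be corrected, because it concerns the decision rule for the primary objective.

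**What to change.** Add to Sections 2.1 and 5.2.1.2.1:

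> Exception: if cohort 2 meets the stopping count, only the 4 mg SD-101 dose is stopped. MK-1966 escalation continues under 3+3 at 210 mg with 1 mg SD-101. If that dose meets the stopping count, the preliminary MTD is 70 mg MK-1966 + 1 mg SD-101 (cohort 1).

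The last part closes the gap over which dose counts as directly below once SD-101 has been reduced. The cost is this short insertion in two sections, with no added subjects or procedures.
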